7.3.2 Secondary Endpoints

Arm A

1. Clinical activity/efficacy: CR, duration of CR, PR, objective response, disease control, TTR, duration of objective response, duration of disease control, PFS, and OS
1. Effect of MEDI-551 on circulating lymphocyte populations: circulating levels of blood mononuclear cells, including T-cells, B-cells, NK cells and monocytes
2. Pharmacokinetics: PK profiles and parameters, including maximum observed concentration (C_{max}), AUC, clearance (CL), and $t_{1/2}$, of MEDI-551
3. Incidence of anti-MEDI-551 antibodies based on samples obtained from each subject at multiple timepoints before and after dosing

Arms B and C

1. Pharmacokinetics: PK profiles and parameters, including C_{max} , AUC, CL, and $t_{1/2}$, of MEDI-551
1. Incidence of anti-MEDI-551 antibodies based on samples obtained from each subject at multiple timepoints before and after dosing
2. Effect of MEDI-551 on B-lymphocyte levels in peripheral blood, including time to recovery of B-lymphocyte level

Arm D

1. Safety: AEs, SAEs, laboratory evaluations, vital signs, physical examinations, and ECGs
2. Pharmacokinetics: PK profiles and parameters, including C_{max} , AUC, CL, and $t_{1/2}$, of MEDI-551
3. Incidence of anti-MEDI-551 antibodies based on samples obtained from each subject at multiple timepoints before and after dosing
4. Effect of MEDI-551 on B-lymphocyte levels in peripheral blood, including time to recovery of B-lymphocyte level

7.3.3 Exploratory Endpoints

Descriptive statistics will be used to describe the exploratory analyses when possible. Depending on the nature of the data, geometric mean and other appropriate statistical summaries might be used as well. The variables likely to be included in the exploratory analyses are described below.

Arm B

1. [REDACTED]

7.4 Assessments

7.4.1 MTD or OBD/Highest Protocol-defined Dose

The MTD was based on the evaluable population for DLT and was defined as the highest dose at which ≤ 1 out of 6 subjects experience a DLT during the DLT evaluation period. The number and percentage of subjects with a DLT will be presented by dose level and overall. Since the MTD was not reached, the OBD (Arm A) or highest protocol-defined dose (Arms B and C) was determined based upon analysis of all available data, including safety, PK, pharmacodynamic, and response.

7.4.2 Safety Assessments

Safety endpoints will be summarized descriptively. The occurrence of AEs, abnormal laboratory values, and SAEs reported from the time that written informed consent is obtained through approximately 90 days post last dose will be summarized for all subjects who received any MEDI-551. Adverse events and SAEs will be graded according to the NCI CTCAE V4.03 and described by system organ class and by Medical Dictionary for Regulatory Activities (MedDRA) preferred term, severity, and relationship to MEDI-551. Frequency rates will be calculated for each system organ class and MedDRA preferred term.

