The primary endpoints of each study arm are as follows: Arm A—MTD defined as the highest dose where ≤ 1 out of 6 subjects experience a DLT during the DLT evaluation period or OBD, and safety of MEDI-551 in relapsed or refractory advanced B-cell malignancies; Arms B and C—MTD defined as the highest dose where ≤ 1 out of 6 subjects experience a DLT during Cycle 1 or highest protocol-specified dose not exceeding MTD: DLTs, safety and tolerability, and clinical activity/efficacy of MEDI-551 as single agent in CLL or combined with rituximab in aggressive lymphomas; and Arm D—clinical activity/efficacy of single-agent MEDI-551 in any anti-CD20-refractory aggressive lymphomas. MTD or OBD/highest protocol-specified dose evaluation was based on the evaluable population for DLT during Cycle 1. The number and percentage of subjects with a DLT will be presented by dose level, and as a group overall. Safety endpoints include assessment of adverse events, serious adverse events, clinical laboratory evaluations, vital signs, physical examinations, and ECGs from the first administration of MEDI-551 through 60 days post-EOT (approximately 90 days after the last dose of MEDI-551). These assessments will be summarized for all subjects who received any MEDI-551. Clinical activity/efficacy will be assessed using CR, duration of CR, objective response, disease control, time to response, duration of objective response, duration of disease control, progression-free survival, and overall survival.

The secondary endpoints of each study arm are as follows: Arm A—clinical activity/efficacy, PK, and IM of MEDI-551 and effect of MEDI-551 on Ig levels and circulating B-lymphocyte populations; Arms B and C—PK and IM of MEDI-551 as single agent or combined with rituximab, and effect of MEDI-551 on lymphocyte populations, including time to recovery of lymphocyte levels; and Arm D—safety and tolerability, PK and IM of single-agent MEDI-551, and effect of MEDI-551 on lymphocyte populations, including time to recovery of lymphocyte levels. Efficacy in Arm A will be assessed as described above for Arms B, C, and D. Safety in Arm D will be assessed as described above for Arms A, B, and C. The PK parameters of MEDI-551 will be estimated using non-compartmental analysis. A population PK analysis may also be performed to obtain additional PK parameters. Anti-MEDI-551 antibodies will be assessed and summarized descriptively by dose cohort for each arm.

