 - Histologically confirmed B-cell NHL (FL or DLBCL): Relapsed from or refractory to ≥ 1 prior regimen containing rituximab, either alone or in combination, and not be a candidate for hematopoietic SCT or BM transplant
 - B-cell CLL: Relapsed from or refractory to ≥ 2 prior lines of treatment, ≥ 1 of which must have contained rituximab
 - Arm B: Relapsed from or refractory to ≥ 2 prior chemotherapy regimens with ≥ 1 regimen containing rituximab
 - Arm C: Relapsed from or refractory to ≥ 2 prior chemotherapy regimens with ≥ 1 regimen containing rituximab or failed 1 prior rituximab-containing regimen and unable to tolerate additional multiagent chemotherapy
 - Arm D: Refractory to ≥ 1 regimen containing any anti-CD20-based therapy, including salvage regimens and maintenance rituximab. Refractory subjects are defined as any subject with less than a PR to any prior anti-CD20-based therapies or progressed within 6 months after completing therapy with any anti-CD20-based regimens, including maintenance rituximab. These subjects must not be eligible for hematopoietic SCT or BM transplant

7. Prior radiation therapy is allowed provided exposure does not exceed an area of 25% of marrow space and occurred ≥ 6 weeks prior to the first dose of MEDI-551 (Arm A only)
8. Karnofsky performance status ≥ 70
9. Life expectancy of ≥ 12 weeks
10. Adequate hematologic function

Arm A (except for CLL subjects with significant BM involvement by biopsy) must meet the following criteria:

- Hemoglobin ≥ 9 g/dL, (≥ 8 g/dL for subjects who are transfusion dependent)
- Absolute neutrophil count $\geq 1500/\text{mm}^3$
- Platelet count $\geq 75,000/\text{mm}^3$

Arms B, C, and D must meet the following criteria:

- Hemoglobin ≥ 8 g/dL
- Absolute neutrophil count $\geq 1000/\text{mm}^3$
- Platelet count $\geq 75,000/\text{mm}^3$
- In the event of significant BM involvement, the above hematologic criteria will not be required for enrollment eligibility

11. Adequate organ function defined as follows:

- Aspartate aminotransferase (AST) and alanine aminotransferase (ALT) $\leq 2 \times$ institutional upper limit of normal (ULN)
- Bilirubin $\leq 1.5 \times$ ULN except for subjects with documented Gilbert's disease, $\leq 2.5 \times$ ULN;
- Serum creatinine ≤ 1.5 mg/dL or a calculated creatinine clearance of ≥ 60 mL/min as determined by the Cockcroft-Gault equation¹

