6 ASSESSMENT OF SAFETY

6.1 Safety Parameters

6.1.1 Adverse Events

The International Council for Harmonisation (ICH) Guideline for Good Clinical Practice (GCP) E6 (R1) defines an AE as:

Any untoward medical occurrence in a patient or clinical investigation subject administered a pharmaceutical product and which does not necessarily have a causal relationship with this treatment. An AE can therefore be any unfavorable and unintended sign (including an abnormal laboratory finding), symptom, or disease temporally associated with the use of a medicinal product, whether or not considered related to the medicinal product.

An AE includes but is not limited to any clinically significant worsening of a subject's pre-existing condition.

Adverse events may be treatment emergent (ie, occurring after initial receipt of investigational product) or nontreatment emergent. A nontreatment-emergent AE is any new sign or symptom, disease, or other untoward medical event that begins after the subject/legal representative signs the informed consent form but before the subject has received investigational product.

Elective treatment or surgery (that was scheduled prior to the subject being enrolled into the study) for a documented pre-existing condition that did not worsen from baseline is not considered an AE.

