6.3 Reporting Requirements for Safety Parameters

6.3.1 Study Reporting Period for Adverse Events

All AEs that occur after a subject has signed the written informed consent form through the 90-Day Post Last Dose Visit must be reported by the investigator.

Any new sign or symptom, disease, or other untoward medical event that occurs after the subject/legal representative signs the informed consent form must be reported by the investigator as an AE in the same way as AEs that occur after the subject receives investigational product.

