7.2 Analysis Populations

The **Evaluable population for DLT** will include all subjects in the dose-escalation phase who receive at least 1 full cycle of MEDI-551 and complete safety follow-up through the DLT evaluation period (defined in Section 4.5.6) or experience any DLT during the DLT evaluation period. The Evaluable population for DLT will be used for the MTD analysis.

The **Safety population** will include all subjects who receive any treatment of MEDI-551. The Safety population will be used to evaluate baseline characteristics as well as all endpoints for safety.

The **Evaluable population for efficacy** will include all subjects who receive any treatment of MEDI-551 and complete at least one post-baseline disease assessment. The Evaluable population for efficacy will be used to evaluate the efficacy endpoints.

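### Section 7.4.2 starts the safety summary at informed consent and the Abstract starts it at the first MEDI-551 dose, so pre-dose events can enter the all-causality safety rates

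*Protocol*

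**What the plan says.** Section 7.4.2 takes adverse events (AEs), abnormal laboratory values and serious adverse events (SAEs) that are "reported from the time that written informed consent is obtained through approximately 90 days post last dose will be summarized" in all subjects given any MEDI-551. Frequency rates follow by system organ class and preferred term.

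The Study Abstract, under Assessment of Endpoints, takes the safety endpoints "from the first administration of MEDI-551 through 60 days post-EOT (approximately 90 days after the last dose of MEDI-551". It adds: "These assessments will be summarized for all subjects who received any MEDI-551". Section 7.2 is consistent with that population: "The Safety population will be used to evaluate baseline characteristics as well as all endpoints for safety".

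Section 6.1.1 has the distinction that would separate the two windows: "Adverse events may be treatment emergent (ie, occurring after initial receipt of investigational product) or nontreatment emergent". It goes on: "A nontreatment-emergent AE is any new sign or symptom, disease, or other untoward medical event that begins after the subject/legal representative signs" consent and before investigational product is received. Section 7.4.2 does not use this distinction.

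Section 6.3.1 sets the collection period: "All AEs that occur after a subject has signed the written informed consent form through the 90-Day Post Last Dose Visit must be reported".

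On blood counts at entry in Arms B, C and D, inclusion criterion 10 in Section 4.2.1 says: "In the event of significant BM involvement, the above hematologic criteria will not be required for enrollment eligibility". The same criterion exempts Arm A subjects with CLL and significant marrow involvement.

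**The concern.** Two current passages define one summary with different starting points, so an analysis that follows either one departs from the other.

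Collecting events from consent is normal practice and is not criticised here. The difficulty is that Section 7.4.2 uses the collection window as the analysis window. A new event during screening then counts in the same frequency table as an event after dosing. The trial has no control group in which such background events would also appear. Section 7.3.1 makes safety a primary endpoint in Arms A, B and C; Section 7.3.2 makes it secondary in Arm D.

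The choice also matters in Arm C for another reason. Section 4.5.2 gives rituximab on Day 1 of Cycle 1 and MEDI-551 first on Day 2. A reaction to rituximab on Day 1 falls inside the 7.4.2 window and outside the Abstract's.

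**Working it through.** There is no sample size, power or alpha figure to reproduce on this point. The check sets the passages side by side.

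| Element | Section 7.4.2 | Study Abstract |
|---|---|---|
| Content | AEs, SAEs, abnormal laboratory values | AEs, SAEs, laboratory evaluations, vital signs, examinations, ECGs |
| Population | Received any MEDI-551 | Received any MEDI-551 |
| Start | Informed consent | First MEDI-551 administration |
| End | About 90 days after last dose | About 90 days after last dose |

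For the items they share, only the start differs.

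**Direction.** The window from consent contains the window from first dose, and the denominator is the same. For any event category, every subject counted from first dose is also counted from consent. All-causality subject counts are therefore equal or larger under 7.4.2, and never smaller.

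**Size.** Let p be the proportion of subjects with an event after first dose and q the proportion with one between consent and first dose. The proportion counted from consent lies between max(p, q) and p + q. If the two were independent it would be 1 − (1 − p)(1 − q).

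The protocol does not give q. As an illustration only, take p from the SAE figure in Section 1.4, 28/111 = 25.2%. The window behind that figure is not stated; it is treated here as post-dose. The values of q are assumptions.

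| Assumed q | Lower bound | Independence | Upper bound |
|---|---|---|---|
| 2% | 25.2% | 26.7% | 27.2% |
| 5% | 25.2% | 29.0% | 30.2% |
| 10% | 25.2% | 32.7% | 35.2% |
| 20% | 25.2% | 40.2% | 45.2% |

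In every row the lower bound is no change at all. It is reached when everyone with a pre-dose event also has one after dosing.

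**Laboratory values.** There are two cases:
- An abnormality seen only before dosing counts under 7.4.2 and not under the Abstract.
- A cytopenia present at entry that persists gives an abnormal value in both windows, so moving the start changes nothing. Only a rule based on worsening from the pre-dose value removes it.

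**Related events and DLTs.** Section 7.4.2 also tabulates by relationship to MEDI-551, and Section 6.2.2 makes timing relative to administration part of that judgement. A pre-dose event should not be called related. Under Section 4.5.6 the DLT period starts at first MEDI-551 administration, so the safety-summary window does not touch the MTD analysis.

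**The case against.** The strongest reply is that this is a wording conflict with little consequence. Safety is summarised descriptively, enrollment is closed, and no dose decision uses these rates. Section 7.1 leaves analysis details to the SAP, which may well specify treatment-emergent tables. These facts limit the weight of the point. They do not remove it, because the protocol has fixed the window twice and differently, and an SAP using either start would contradict one of the two passages.

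Some stronger readings are tempting, and the documents do not support them:

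- *Baseline cytopenias inflate the AE rates because of the window.* Section 6.1.1 limits nontreatment-emergent AEs to new findings and counts a pre-existing condition only on clinically significant worsening. Section 5.3.1 assigns baseline grades to history and examination findings and counts only increases in severity. Pre-existing cytopenias are thus largely kept out of AE counts. They enter through the abnormal laboratory values, and persistent ones do so under either window.
- *Pre-dose events would be attributed to MEDI-551.* The relationship assessment guards against this, and Section 6.2.4 requires a separate protocol-relatedness assessment for SAEs before dosing. Only all-causality counts can move.
- *An assumed prevalence times enrollment gives the inflation.* If 5% to 25% of subjects had a pre-dose abnormality (an assumption), that would be 7 to 34 of the 137 enrolled (26 + 69 + 7 + 19 + 16), or 6 to 30 of the 121 in Arms A to C (137 − 16). This is only a ceiling. A subject adds to the rate only if no qualifying abnormality occurs after dosing.

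**Conclusion.** The inconsistency stands and should be corrected. Section 7.4.2 and the Abstract define the same safety summary, in the same treated population and to the same end, from different starting points. Following 7.4.2 counts new events between consent and first dose, and pre-dose laboratory abnormalities, in the all-causality rates.

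The direction is certain, since it rests only on one window containing the other with a common denominator. The size is unknown and may be zero; the illustrated percentages depend on assumed pre-dose rates and are not estimates for this trial. Rates of MEDI-551-related events and the DLT and MTD conclusions are essentially unaffected. The point concerns clear reporting of a descriptive endpoint that is primary in Arms A to C and secondary in Arm D. It does not threaten the trial's conclusions on dose.

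**What to change.** Amend Section 7.4.2 and the Abstract together so that they agree:

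1. Base the main AE and SAE summaries on treatment-emergent events, meaning onset or worsening after first dose, through about 90 days after last dose. List events between consent and first dose separately.
2. Summarise laboratory abnormalities as post-baseline worsening from the pre-dose value. A new start date alone would leave persistent baseline cytopenias in the tables.
3. For Arm C, state that the window opens at the first dose of either study drug, which is rituximab on Day 1, so that Day 1 reactions stay in the combination safety summary. Say openly that this departs from the Abstract, which names MEDI-551 only, and from Section 6.1.1, which refers to the investigational product. Copying the Abstract's wording into 7.4.2 would move those reactions out.

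The cost is a few sentences of analysis text. The events are already collected from consent, and the treatment-emergent concept is already in Section 6.1.1; only its Arm C starting point needs new wording. No new assessment or data collection is needed.

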7.4.3 Efficacy Assessments

The efficacy will be assessed based on CR, duration of CR, objective response, disease control, TTR, duration of objective response, duration of disease control, PFS, and OS.

- **Complete response:** The definition of CR varies by disease type (see Section 5.3.6).
- **MRD-negative CR:** Subjects with CR and negative MRD defined as the proportion of subjects with a best response of CR and without MRD.
- **Duration of complete response:** Duration of CR will be measured from the first documentation of a CR to the time of PD/relapse. Duration of CR will be censored on the date of last disease assessment for subjects who have no documented relapse prior to data cutoff, dropout, or the initiation of alternative anticancer therapy. Duration of CR will only be calculated for the subgroup of subjects with CR using the Kaplan-Meier method.
- **Objective response:** Objective response includes CR and PR.
- **Disease control:** Disease control includes CR, PR, or SD for at least 8 weeks.
- **Time to response:** Time to response will be measured from the start of MEDI-551 administration to the first documentation of response (CR or PR) and will only be assessed in subjects who have achieved objective response.

- **Duration of objective response:** Duration of objective response will be measured from the first documentation of objective response to the event of PD/relapse. Duration of objective response will be censored on the date of last disease assessment for subjects who have no documented relapse prior to data cutoff, dropout, or the initiation of alternative anticancer therapy. Duration of objective response will only be calculated for the subgroup of subjects with an objective response.
- **Duration of disease control:** Duration of disease control will be defined as the time period from start of MEDI-551 administration to the event of PD/relapse. Duration of disease control will be censored on the date of last disease assessment for subjects who have no documented PD/relapse prior to data cutoff, dropout, or the initiation of alternative anticancer therapy. Duration of disease control will only be calculated for the subgroup of subjects with best response of CR, PR, or SD.
- **Progression-free survival:** Progression-free survival will be measured from start of MEDI-551 administration until the first documentation of PD/relapse or death, whichever occurs first. Progression-free survival will be censored on the date of last disease assessment for subjects who have no documented PD/relapse or death prior to data cutoff, dropout, or the initiation of alternative anticancer therapy.
- **Overall survival:** Overall survival will be determined as the time from the start of MEDI-551 administration until death. For subjects who are alive at the end of study or lost to follow-up, OS will be censored on the last date when subjects are known to be alive.

The analysis methods will differ by the types of endpoints. For categorical endpoints, proportions will be summarized, 80% and 95% confidence intervals will be calculated using the Clopper-Pearson exact method. For time-to-event endpoints, Kaplan-Meier method will be used to describe the endpoints graphically and to estimate the median or the event rates at time of interest.

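### Durations of CR, objective response and disease control end only at PD/relapse, so a death without documented PD is censored; report a PD-or-death version alongside

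*Protocol*

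**What the plan says.** Protocol section 7.4.3 defines three durations, each ending at progression or relapse:

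- For CR, the rule is: "Duration of CR will be measured from the first documentation of a CR to the time of PD/relapse".
- For objective response, the rule is: "Duration of objective response will be measured from the first documentation of objective response to the event of PD/relapse".
- For disease control, the rule is: "Duration of disease control will be defined as the time period from start of MEDI-551 administration to the event of PD/relapse". It is restricted to a subgroup: "Duration of disease control will only be calculated for the subgroup of subjects with best response of CR, PR, or SD".

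The censoring clauses follow the same pattern. For objective response: "Duration of objective response will be censored on the date of last disease assessment for subjects who have no documented relapse"; the clause for CR is worded alike. For disease control: "Duration of disease control will be censored on the date of last disease assessment for subjects who have no documented PD/relapse". The closing conditions are data cutoff, dropout or start of another anticancer therapy. Death appears neither as an event nor as a censoring reason.

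PFS, in the same section, ends at PD/relapse or death, whichever is first, and its censoring clause includes death: "Progression-free survival will be censored on the date of last disease assessment for subjects who have no documented PD/relapse or death". For all time-to-event endpoints the "Kaplan-Meier method will be used to describe the endpoints graphically and to estimate the median or the event rates at time of interest".

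Sections 7.3.1 and 7.3.2 list the three durations among the primary endpoints of Arms B, C and D and the secondary endpoints of Arm A.

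**The concern.** A responder who dies without documented PD satisfies the condition of having no documented relapse, so the rule censors that subject at the last disease assessment. Reading death as a form of dropout gives the same result. The same death, if it precedes cutoff, dropout and new therapy, is an event for PFS.

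Kaplan-Meier treats censored subjects as if they would go on to progress at the same rate as those still under observation. A subject who has died cannot. The curve therefore describes time to progression with deaths removed, while a reader is likely to take a duration of response as time alive and in response. The estimates will usually be as long as, or longer than, those with death counted. PFS and OS do not fill the gap, because both start at first dose and neither is restricted to responders.

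**Working it through.** **Comparing the definitions.** The protocol gives no figure to reproduce here; the first check is of wording.

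| Endpoint | Start | Event | Death without documented PD |
|---|---|---|---|
| Duration of CR | first CR | PD/relapse | censored at last assessment |
| Duration of objective response | first response | PD/relapse | censored at last assessment |
| Duration of disease control | first dose | PD/relapse | censored at last assessment |
| PFS | first dose | PD/relapse or death | event |

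Within the CR/PR/SD subgroup, duration of disease control and PFS share the start and the stated censoring reasons. Only the treatment of death separates them.

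**Inputs for an illustration of size.**

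- Deaths: 27 of 111 subjects at the 31Mar2015 cutoff (27/111 = 24.3%), PD being the most common cause (section 1.4). The number without documented PD is not given.
- Preliminary duration of response in Arm A aggressive lymphoma: about 5 months (section 1.5). Its event definition is not stated; it is *assumed* to be a progression-only median.
- Responders: 7 in Arm C and 3 in Arm D (section 7.5). For Arm A, 19% of 26 + 29% of 34 + 23% of 26 ≈ 5 + 10 + 6 = 21, pooled by assumption (section 1.5).
- Assessments every 2 months with a ±7-day window (Table 5.2.1-1).
- f, the share of first events that are deaths without documented PD: *assumed* 5%, 10%, 20%, 30%.

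**Closed form, constant hazards.** The PD hazard is ln 2/5 per month and the total hazard is (ln 2/5)/(1 − f). The PD-or-death median is therefore 5(1 − f), and the 6-month rate is 0.5^(6/median). The chance that at least one of n responders is affected is 1 − (1 − f)^n.

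| f | PD-or-death median (months) | 6-month rate (PD-only 43.5%) | Chance ≥ 1 affected, n = 7 | n = 3 |
|---|---|---|---|---|
| 5% | 4.75 | 41.7% | 30% | 14% |
| 10% | 4.5 | 39.7% | 52% | 27% |
| 20% | 4.0 | 35.4% | 79% | 49% |
| 30% | 3.5 | 30.5% | 92% | 66% |

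**Simulated Kaplan-Meier medians.** Event times are exponential at the total hazard, and an event is a death with probability f. PD is dated at the next 2-monthly visit, with each visit shifted uniformly within ±7 days. Follow-up is complete. There were 20,000 runs (6,000 for n = 21). Each run compares the median with deaths censored at the last visit and with deaths counted. Entries give the percentage of runs in which the PD-only median is longer / shorter / unchanged.

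| f | n = 7 | n = 3 | n = 21 |
|---|---|---|---|
| 5% | 9.6 / 0.3 / 90.1 | 3.3 / 1.0 / 95.6 | 28.6 / 0.1 / 71.4 |
| 10% | 18.9 / 0.6 / 80.4 | 6.7 / 2.0 / 91.3 | 52.7 / 0.1 / 47.2 |
| 20% | 35.9 / 1.2 / 62.9 | 13.5 / 3.7 / 82.8 | 81.7 / 0.2 / 18.2 |
| 30% | 51.5 / 1.5 / 46.9 | 21.4 / 5.4 / 73.3 | 93.5 / 0.2 / 6.3 |

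At n = 21, the typical lengthening in the runs where the median is longer is about 0.2 month at f = 5% and 10%, 0.9 month at 20% and 1.7 months at 30%.

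**Direction.** Longer is usual but not certain, because the subject leaves the risk set at the last assessment, before the death. Example: A is last assessed at 2 months and dies at 7; B has PD at 4; C has PD at 8.

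- Progression only: at 4 months two are at risk, survival falls to 1/2, and the median is 4.
- PD or death: survival is 2/3 at 4 months and 1/3 at 7, and the median is 7.

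**The case against.** The best case for leaving the text alone is that nothing in it is misstated. Each duration has a stated origin, event and censoring rule, and PFS is a separate endpoint that may use a different event. Progression-only duration of response is recognised; the appended rituximab label uses it (Appendix 2, label Table 4, footnote d). Section 7.1 leaves analysis details to the SAP, which may add a second version. PFS and OS already count deaths in every arm, and a PD-or-death duration of disease control is simply PFS within the CR/PR/SD subgroup.

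The size is also uncertain. f may be 0, and the 27 deaths cover all subjects, not responders. At low f the medians for 7 or 3 responders are unchanged in most runs. At n = 21 the low-f shifts of about 0.2 month lie within the assumed visit window. The 5-month figure comes from aggressive lymphoma and is stretched over a pool in which about 15 of 21 responders had CLL or FL. The Version 13.0 summary in section 15 reports responses beyond 1 year for Arm A subjects who stopped treatment in CR. Full follow-up is assumed, although Version 13.0 ends long-term follow-up.

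Most of this stands, and it limits the weight of the point. It does not remove it. The event and censoring rules are fixed in the protocol itself, and no analysis stated there gives time from response to PD or death. That the SAP adds one cannot be excluded.

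**Conclusion.** The point holds as a worthwhile improvement, not a critical flaw. Under section 7.4.3 a death without documented PD is censored for all three durations while counting for PFS, so the Kaplan-Meier results estimate time to progression. If the preliminary 5 months is a progression-only median and hazards are constant, counting death gives 4.75 months at f = 5% and 3.5 months at f = 30%. If no responder died without documented PD, nothing changes.

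The reach is limited. Sample sizes rest on the CR rate (Arm A) or the response rate (Arms B, C and D), and no hypothesis or halting decision uses these durations. The Arm B expansion was not conducted, and Arms C and D have only 7 and 3 responders. The reading of the definitions is firm; the size depends on a count the protocol does not give.

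**What to change.** In section 7.4.3, keep the three prespecified durations and label them as time to progression with deaths censored. Add one sentence: each duration will also be reported with the event defined as the first of PD/relapse or death from any cause, using the PFS censoring rules. State that these versions were added after enrollment closed on 30Sep2015 and with responses known.

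The cost is one sentence and a label, since death dates are already needed for PFS and OS. The added durations may be shorter than the prespecified ones, and the addition is late, hence the disclosure. Once Version 13.0 is in effect, deaths are followed only to the 90-Day Post Last Dose Visit, the same limit that applies to PFS.
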